8.0 Procedures Involved

8.1 *Describe and explain the study design:*

This is a crossover design and within-subjects analysis plan where participants receive all conditions during the flavor-nutrient conditioning paradigm of Aim 1. A subset of participants will also undergo fMRI scanning for Aim 1. All participants will undergo the controlled feeding diet and metabolic chamber measurements for Aim 2.

8.2 *Provide a description of:*

- *All research procedures being performed*
- *If the study has more than one procedure, session, and/or subject population, describe each procedure, session, and/or study population separately. For complex studies, you are encouraged to include a figure or chart.*

Study Overview:

Approximately 15 people from the general population will be recruited for Aim 1 (without fMRI) and Aim 2 of this randomized crossover design study conducted at FBRI. Of these 15 people, 5 will also undergo fMRI scanning as a part of Aim 1. This will be an approximately 6- to 7-week study. Participants will report to the research laboratory in Week 1 for the consent and training session. They will return to the research laboratory to complete 2 behavior sessions per beverage and a final post-testing session in Aim 1. Participants who are asked to complete the fMRI scan will undergo this measurement during the final post-testing session. For Aim 2, participants will report to the metabolic kitchen at FBRI for 2 days preceding each chamber measurement day to collect food to be consumed for each of those days. On each metabolic chamber measurement day, they will report to the metabolic chambers located in [name]. There will be a 5-day washout period between the first metabolic chamber session and controlled feeding for the second metabolic chamber session.

Recruitment and Screening:

Approved study recruitment materials will be distributed in the follow ways. Flyers will be posted on bulletin boards and approved posting sites throughout Roanoke, Blacksburg, and surrounding areas. Digital advertisements will be displayed on [name] lab and CHBR social media, VT News, and in list serves with permission.

PROTOCOL (STUDY) TITLE AND NUMBER

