At the end of this session, participants will be given 2 additional bottles containing 355 ml of the beverage consumed during this session. Participants will be instructed to consume one beverage 1 hour before dinner that evening and the other beverage 1 hour before lunch the following day. Participants will also be asked to complete a short survey regarding consumption of each of these beverages. An automated email containing links

PROTOCOL (STUDY) TITLE AND NUMBER

to a survey about the dinner and lunch beverage consumption will be sent using the same REDCap automated email function described above.

Post-Testing Session (for participants NOT undergoing fMRI portion of the protocol):
Participants will come to the CHBR after a 4 hour fast. Participants will also be asked to abstain from moderate-to-vigorous physical activity for at least 24h prior to their session. They will first rate their internal states on standard scales.

They will then taste and rate on standard scales the 2 flavors they consumed as part of the conditioning beverages throughout the protocol. After the rating, they will be given access to bottles containing the two they consumed during the protocol sessions and allowed to drink as much or as little as they want from the 2 bottles for 30 minutes. Consumed amounts of each beverage will be measured and recorded. Lastly, they will be offered 2 additional bottles containing the same conditioning beverages and allowed to choose one to take home with them in a forced-choice test.

Post-Testing Session (for participants who ARE undergoing fMRI portion of the protocol):

Participants completing the fMRI portion of the protocol will first report to the CHBR after a 4 hour fast. Participants will also be asked to abstain from moderate-to-vigorous physical activity for at least 24h prior to their session. They will first rate their internal states on standard scales. Then, they will be escorted to the Human Neuroimaging Laboratory in [name] for the fMRI scan.

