During this scan, participants will lie on a table that slides into the bore of the scanner. Using a head coil, the functional images will be acquired using an EPI bold sequence. Because the process is noisy (due to the sounds generated as the magnetic field gradients are changed), participants will wear a pair of headphones and disposable earplugs. During the entirety of the scan, subjects will be able to communicate with the experimenter via a speaker and microphone system. If subjects become uncomfortable or claustrophobic while in the scanner, they will be able to squeeze an emergency ball to get the attention of the experimenters who will then immediately remove them from the scanner. They can then withdraw from the study if they are unable to complete the MRI.

While in the magnet, subjects will taste small amounts of liquid stimuli that will be presented according to a standard paradigm we have successfully used before in taste MRI studies (Small et al., 2003; Small et al., 2004). In brief, hydraulic pumps will be used to pump solutions through plastic beverage tubing attached to a mouthpiece to the subject lying in the scanner. The mouthpiece will be sterilized and new beverage tubing will be used for each subject. The mouthpiece will be anchored to the head coil so that the end comfortably rests on the anterior tongue, just inside the subjects' mouth. This will not interfere with breathing through the mouth and subjects will always be able to breathe through their noses. To ensure participants can breathe through their nose, they will be asked to close their mouth and take one full breath (inhale and exhale) through their nose. If they are unable to breathe normally through their nose on the day of the scan, the scan will be rescheduled. The solutions will be dispensed through one tube at a time. The

PROTOCOL (STUDY) TITLE AND NUMBER

overall flow rate of solution into the mouth will be very slow (0.5ml of a liquid over 3-5 seconds). Each taste will be followed by a rinse of a tasteless solution.

After the fMRI is completed, they will be given access to bottles containing the two they consumed during the protocol sessions and allowed to drink as much or as little as they want from the 2 bottles for 30 minutes. Consumed amounts of each beverage will be measured and recorded. Lastly, they will be offered 2 additional bottles containing the same conditioning beverages and allowed to choose one to take home with them in a forced-choice test.

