11.0 Study Timelines

PROTOCOL (STUDY) TITLE AND NUMBER

11.1 *Describe:*

- *The duration of an individual subject's participation in the study (for example, 1 hour, 2-4 weeks, 3-5 years).*
- *The amount of time expected to enroll all study subjects (weeks, months, years, etc.)*
- *The amount of time expected for the investigators to complete this study including primary data analyses.*

Consent and Training Session: 2 hours

Behavior Sessions 1-4: 2 hours each (8 hours total)

Post-Testing Session without fMRI: 1 hour

Post-Testing Session with fMRI: 3 hours

Metabolic Chamber Sessions 1 and 2: 6 hours each (12 hours total)

Each participant is expected to be enrolled for approximately 8-10 weeks.

The study, including recruitment, enrollment, and primary data analysis, is expected to last 1 year.

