12.0 Inclusion and Exclusion Criteria

12.1 *Describe how you will screen individuals for eligibility. When will screening occur and what procedures will you use? Upload any screening scripts or surveys to Protocol Management:*

Participants will complete an online screening survey after they have indicated interest in participating in the study. A link to the Ripple survey will be sent to participants via email, or they can access the link through a written web address or QR code on our flyer. Additionally, social media posts will contain the web address. Participants undergoing fMRI will also complete an MRI screening form.

12.2 *Describe the eligibility criteria that define who will be included and who will be excluded from enrollment for each procedure of your study.*

Include any geographic criteria (e.g., Virginia Tech undergraduate students, a national sample of adults with engineering degrees, minors aged 8-12 in the New River Valley, university faculty in Virginia and Paris, France):

PROTOCOL (STUDY) TITLE AND NUMBER

Inclusion Criteria:

1. Age 18-45 years
2. BMI between 18.5-40 kg/m²
3. Not pregnant or planning to become pregnant during study participation
4. Residing in the Roanoke area and/or willing/able to attend sessions at FBRI
5. Able to speak and write in English
6. Specific to fMRI scan only: BMI >25 kg/m²

Exclusion Criteria:

1. Current inhaled nicotine use
2. History of alcohol dependence.
3. Current or past diagnosis of diabetes, or thyroid problems.
4. Hemoglobin A1C >5.7%
5. Taking medications known to influence study measures (including antiglycemic agents, thyroid medications, sleep medications)
6. Active medical or neurologic disorder.
7. Recent change in body weight (gain or loss of > 5 lbs within the past 3 months)
8. Current shift work (typical pattern of work/activity overnight)
9. Previous weight loss surgery
10. Adherence to a special diet within the past 3 months (e.g., low-carb or ketogenic diet, exclusion of food groups/specific macronutrients, intermittent fasting, etc.)
11. Allergy to any food or ingredient included in the study diets, meals, or beverages
12. Currently pregnant or planning to become pregnant during study participation
13. Claustrophobia

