15.2 Describe the source of subjects (for example, clinic patients with specific conditions, students in the library, community members at a gathering, or members of a local gym):

Participants will be recruited from the general public.

15.3 Describe the methods that you will use to identify potential subjects:

Responses on the online screening form will be used to identify potential subjects.

PROTOCOL (STUDY) TITLE AND NUMBER

15.4 Describe materials that you will be use to recruit subjects. Attach copies of these documents with this protocol in Protocol Management and be sure to include the IRB protocol number on each document.

- *For flyers, attach the final copy of printed flyers.*
- *For Virginia Tech News, Facebook postings and ads, newspaper ads, websites, MTurk/SONA/online survey systems, etc., attach the final wording and graphics to be used.*
- *For email recruitments, please include the subject line.*
- *For advertisements meant for audio broadcast, please submit the wording of the advertisement prior to taping (to avoid having to re-record with approved language) and submit the final recorded version for IRB review before use.*
- *Describe any compensation to subjects. Separate compensation into appropriate categories, such as: reimbursement for expenses, time and effort, and additional incentives for study participation. For each category, specify the amount (including any pro-rated amount), schedule, and method of payment.*

See above in 15.3 for a list of recruitment materials and methods that will be used.

Consent and Training Session (2 hrs) - \$40

Behavior Sessions 1-4 (2 ½ hours each) - \$50 each session, up to \$200 total

Post-Test Session (1 hour) - \$20

fMRI Scan (2 hours) - \$40

Metabolic Chamber Sessions 1-2 (6 hours each)- \$120 each session, up to \$240 total

Total (with fMRI scan): up to \$540

Total (without fMRI scan): up to \$500

Participants will be paid via ClinCard, a prepaid Mastercard that we will provide them at the end of the first session. Participants will be compensated at the end of each visit using the ClinCard system.

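### Scanned participants, all with BMI above 25, take the intake and choice tests about 2 hours later than the others and after in-scanner tasting, so test conditions are partly confounded with BMI

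*Combined protocol and SAP*

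**What the plan says.** Section 8.2 describes two post-testing sessions. Both begin with a 4-hour fast and a rating of internal states on arrival.

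- **Not scanned:** participants taste and rate the two flavors, and then "After the rating, they will be given access to bottles containing the two they consumed during the protocol sessions". A 30-minute intake test and a forced choice follow.
- **Scanned:** participants go to the imaging laboratory and receive 0.5 ml tastes in the scanner, each followed by a rinse. Then: "After the fMRI is completed, they will be given access to bottles containing the two they consumed during the protocol sessions". The same intake test and forced choice follow. No second rating of internal states is described.

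Section 11.1 gives the lengths: "Post-Testing Session without fMRI: 1 hour" and "Post-Testing Session with fMRI: 3 hours". Section 15.4 pays the scan as a separate 2-hour item.

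The study enrolls "BMI between 18.5-40 kg/m²", but 12.2 adds "Specific to fMRI scan only: BMI >25 kg/m²". On numbers, 8.2 says "Of these 15 people, 5 will also undergo fMRI scanning as a part of Aim 1".

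Section 4.1 lists drink preference among the primary endpoints, and 2.2 hypothesizes poorer reinforcement learning with increasing obesity. Section 5.2 plans mixed models for beverage ratings with adjustment for confounders. It names no confounder and gives no model for intake or choice.

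**The concern.** The same outcome is measured under conditions that depend on scan status, and scan status depends on BMI. Nobody at BMI 25 or below can be tested after a scan. If a longer fast, thirst or repeated tasting changes how much people drink or which drink they favor, part of that change will look like a BMI difference. BMI is the characteristic the hypothesis is about. With no rating of hunger or thirst just before intake, the analyst could not later check whether the two groups started the test in the same state.

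**Working it through.** **Difference in timing.** From 11.1, 3 h − 1 h = 2 h. This agrees with 15.4, where a 1 h post-test plus a 2 h scan makes 3 h. The scanned group therefore starts intake at roughly 4 + 2 = 6 hours fasted, against a little over 4 hours for the others. The 2 hours is a scheduled slot that may include set-up; time in the magnet and the number of tastes are not stated.

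**One post-test per person?** The totals in 15.4 reproduce with a single $20 post-test: 40 + 200 + 20 + 240 = 500 without the scan, and 500 + 40 = 540 with it. The subset/majority wording in the Study Summary and the session titles in 8.2 point the same way, giving 15 − 5 = 10 unscanned and 5 scanned. Section 14.4, however, lists 15 for the post-test without fMRI and 5 for the one with it.

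**Share of a scan-condition effect that enters a BMI contrast.** Let k of the 15 completers have BMI above 25. The documents give no BMI distribution, so k is an assumption. All five scanned participants are among the k, and none is among the 15 − k. Let D be the effect of the post-scan conditions on the outcome analysed (total intake, or the sugar-minus-sucralose difference).

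- Bias in the unadjusted group contrast: (5/k)·D − 0·D = (5/k)·D.
- Correlation of scan status with BMI group: phi = √[(15 − k)/(2k)]. At k=8, √(7/16) = 0.66.
- Variance multiplier for the BMI contrast after adjusting for scan status: 1/(1 − phi²). At k=8, 1/(1 − 0.4375) = 1.78.

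| k above BMI 25 | share of D | phi | variance multiplier |
|---|---|---|---|
| 5 | 1.00 | 1.00 | not estimable |
| 6 | 0.83 | 0.87 | 4.00 |
| 8 | 0.63 | 0.66 | 1.78 |
| 10 | 0.50 | 0.50 | 1.33 |
| 12 | 0.42 | 0.35 | 1.14 |

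Leaving out the scanned five costs the same precision in this two-group comparison. At k=8, (1/3 + 1/7)/(1/8 + 1/7) = 0.476/0.268 = 1.78.

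For BMI as a continuous variable, a simulation that assumed BMI uniform on 18.5–40 gave a mean correlation with scan status of about 0.38.

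**The case against.** The strongest reply is that preference is a within-person contrast. Both bottles are on offer during the same 30 minutes, and the choice is between the same two drinks. A delay that shifts drinking of both equally cancels in the sugar-minus-sucralose difference. This stands. A reader might infer that any effect of fasting, thirst or tasting must appear as a BMI effect on preference, but the design does not support that. It would need the post-scan conditions to act differently on the two drinks, which is possible (a longer fast could favor the caloric one) but not shown. Total intake has no such protection.

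A reader might also take the BMI comparison of intake and choice to be the planned test of the hypothesis. Section 5.2 specifies no such analysis, and the primary objective is feasibility in a 15-person pilot. That limits the consequence. It does not remove the problem for anyone who later relates these data to BMI, and section 3.3 intends the data as evidence on the gut-brain axis across BMI.

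Three smaller points have some force:

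- Unscanned participants also taste both flavors just before intake, so the tasting difference is one of degree.
- Section 9.1 mentions storing the time food was last eaten before measurement. The context is indirect calorimetry, so whether this covers the post-test is uncertain, and it would not capture thirst or hunger.
- The general promise in 5.2 to adjust for confounders could cover scan status, but it is made for ratings and names nothing.

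**Conclusion.** The concern holds as partial confounding. Five of 15 completers take the intake and choice tests about 2 hours later and after scanner tasting, and all five have BMI above 25. The beverage main effect is not confounded with BMI. At risk are BMI comparisons of total intake, and BMI-by-beverage comparisons of preference or choice if the two drinks are affected differently.

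The share of D that enters an unadjusted group contrast runs from 1.00 at k=5 to 0.42 at k=12. It rests on the assumed k and on splitting BMI at 25. The size and direction of D are unknown. A reader might infer that BMI and scan effects cannot be separated. For the group contrast that is true only at k=5; with any unscanned participant above 25, adjustment is possible at a cost in precision. At k=15 there is no BMI-group contrast to bias.

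For a feasibility pilot this is a low-cost improvement, not a flaw that undermines the study.

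**What to change.** - **Section 8.2, both post-testing sessions:** repeat the internal-state ratings immediately before the intake test in every participant, and record the time since last intake.
- **Section 5.2:** report any BMI analysis of intake, preference and choice with and without the five scanned participants, or with scan status as a covariate where k allows. State the different test conditions as a limitation.
- **Section 14.4:** reconcile the post-test counts (15 without fMRI, 5 with) with the one-session-per-person reading of the Study Summary and 8.2.

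The cost is about a minute of rating per participant and one sensitivity analysis with reduced precision (variance of the BMI contrast multiplied by 1.78 at k=8).

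Moving the scan to a separate day is optional. If intake comes first, the scanned five have free access to both drinks before brain activation is measured. If the scan comes first, scanner tasting still precedes intake in that subset only. Either order adds exposure to the drinks before one of the primary endpoints, and it means a further fasted visit for five people.

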9.0 Data and Specimen Long Term Storage and Use

9.1 *If you will store data or specimens for future use, describe where you will store the data or specimens, how long they will be stored, and how and by whom the data or specimens will be accessed:*

Indirect calorimetry data and 24-hour food recall data will be stored on a secure network drive provided by FBRI. Behavioral (e.g., last time food eaten before measurement, last bout of exercise before measurement, etc.), anthropometric, responses to questionnaires, and pertinent energy expenditure variables collected during indirect calorimetry measurement will be stored in FBRI's instance of REDCap. Data will be stored indefinitely for future analysis and use in developing future protocols using indirect calorimetry methods. Only individuals with FBRI access to secure network drives and FBRI's instance of REDCap will have access to stored data. Plasma and/or serum aliquot samples will be frozen and stored for future analysis of insulin. As it is more cost effective to run an ELISA or Immulite 1000 with a full number of wells, these samples will be stored until they can be analyzed in batch. Additional aliquots of plasma and/or serum will be stored indefinitely after the completion of data analysis to allow for replicate testing to ensure data quality and for additional analyses as the field moves forward.

9.2 *For specimens, list the data to be stored or associated with each specimen:*

PROTOCOL (STUDY) TITLE AND NUMBER

Only a 4 digit number will be used to label data and the date collected.

9.3 *Describe the procedures to release data or specimens outside of the research team, including the process to request a release, approvals required for release, who can obtain data or specimens, and what data will be provided with specimens:*

No specimens will be released.

9.4 *Describe the identifiers to be included with stored data or specimens, as well as any key or code that could be used to make them identifiable. Describe where the code will be stored, who will have access to it, and when it will be destroyed:*

Data will be coded using a 4 digit number. Participant IDs will be created sequentially starting at 9999. The key linking the participant name or identifiable information and the code will be stored on an encrypted server managed by the FBRI IT department. This server can only be accessed by those on the research team. All study data will be kept on a separate server from identifiable information, also encrypted. Any paper documents generated that contain other identifiers, such as name, phone number, or email will be stored in a locked file cabinet accessible only by authorized staff.

Identifiable participant information will be destroyed 5 years after publication or at the written request of the participant.

Per Virginia Tech policy, in order to compensate participants, social security number (or Taxpayer ID) and street address will be collected via a W-9 form or W-8BEN. The participant address and SSN will be entered into the ClinCard systems, which is a HIPAA compliant payment system approved by Virginia Tech. After entry, this form will be given to and stored by the central administration at the FBRI to be used if it is required that a tax statement be sent to the participant, based on Federal Income Tax regulations. Study staff will not store any documents with SSN or address used for payment purposes.

9.5 *Please select the identifiers you will obtain (whether directly from participants or from another source), including but not limited to:*

	Name
--------------------------	-------------

PROTOCOL (STUDY) TITLE AND NUMBER

	Geographical subdivisions smaller than a state, including street address, city, county, precinct, zip code, and equivalent geocodes (note, the initial three digits of a zip code are not considered identifiable)
	Elements of dates (except year) for dates directly related to an individual, including birth date, admission date, discharge date, date of death, and single year of age over 89 and all elements of dates (including year) indicative of such age (note, such ages and elements may be aggregated into a single category of age 90+)
	Phone numbers
	Fax numbers
	Electronic mail addresses (e-mail)
	Social Security numbers
	Medical record numbers
	Health plan beneficiary numbers
	Account numbers
	Certificate/license numbers
	Vehicle identifiers and serial numbers, including license plate numbers
	Device identifiers and serial numbers
	Web Universal Resource Locators (URLs)
	Internet protocol (IP) address numbers
	Biometric identifiers, including finger and voice prints (audio recording)
	Full face photographic images and any comparable images (including video recording)
	Student record number or identification number
	User name for online or computer accounts
	Any other unique identifying number, characteristic, or code (note this does not mean the unique code assigned by the investigator to code the data): Click here to explain.

